14.2. Sample Size Justification

A total of approximately 80 eligible subjects will be enrolled into the study at this site and at least 60 subjects will complete this study. This is a pilot study for assessing the test articles. As such, the sample size calculation was not based on any power analysis with regard to the primary endpoint. The collected data will be used to design future trials.

14.3. Analysis Populations

Safety Population:

All subjects who were administered any test article excluding subjects who drop out prior to administering any test article. At least one observation should be recorded.

Per-Protocol Population:

All subjects who have successfully completed all visits and did not substantially deviate from the protocol as determined by the trial cohort review committee prior to database hard lock (Per-Protocol Population). Justification of excluding subjects with protocol deviations in the per-protocol population set will be documented in a memo to file.

Intent-to-Treat (ITT) Population:

All randomized subjects regardless of actual treatment and subsequent withdrawal from study or deviation from protocol. At least one observation should be recorded.

14.4. Level of Statistical Significance

All planned analysis for this study will be conducted with an overall type I error rate of 5%. No adjustment for multiple comparisons will be conducted unless specified otherwise. This is a pilot study and all the hypotheses are exploratory in nature.

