2.3. Hypotheses

Primary Hypotheses

1. After 8-12 days of lens wear, the distance, binocular, high luminance, high contrast visual performance of the two test lenses will be superior to +0.01 logMAR.
2. After 8-12 days of lens wear, the near, binocular, high luminance, high contrast visual performance of the two test lenses will be superior to +0.17 logMAR.

Secondary Hypothesis

1. After 8-12 days of lens wear, the overall quality of vision of the two test lenses will be superior to 32 CLUE points.

Other Hypotheses: Not applicable.

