14.5. Primary Analysis

Primary efficacy analysis:

Visual Performance:

Near and distance binocular, high luminance, high contrast visual performance on logMAR scale will be analyzed separately using a linear mixed model to test for the difference between the study lens systems. Each model will include the experimental design factors: sequence of lens wear, lens wearing period and lens type as fixed effects. Other baseline characteristics known of importance such as age, gender, and/or add power will be included as fixed covariates when appropriate. The covariance between residual errors from the same subject across lens wearing periods will be selected based on the finite-sample corrected Akaike's Information Criterion (Keselman et al. 1998). Covariance structures considered may include: Homogenous compound symmetry (CS) and Unstructured covariance structure (UN). The structure that returns the lowest Akaike Information Criteria Corrected (AICC) will be selected as the structure that best fit the data.

Comparisons will be carried out using 95% confidence intervals constructed of least squared means (LSM) from the linear mixed models. Statistical superiority will be concluded if the upper limit of the confidence intervals of the test lens is below +0.01 logMAR for distance and +0.17 for near.

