14.6. Secondary Analysis

CLUE Vision Score:

Overall quality of vision scores will be analyzed using a linear mixed model adjusting for baseline values as fixed covariates. The model will include the experimental design factors: sequence of lens wear, period, lens type as fixed effects. The covariance between residual errors from the same subject across lens wearing periods will be selected based on the finite-sample corrected Akaike's Information Criterion (Keselman et al. 1998). Covariance structures considered may include: Homogenous compound symmetry (CS) and Unstructured covariance structure (UN). The structure that returns the lowest Akaike Information Criteria Corrected (AICC) will be selected as the structure that best fit the data.

Comparisons will be carried out using 95% confidence intervals constructed of least squared means (LSM) from the linear mixed models. Statistical superiority will be concluded if the lower limit of the confidence intervals of the test lens is above 32 points.

In all models, the Kenward and Roger method (Kenward and Roger, 1997) will be used for the calculation of the denominator of degrees of freedom.

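### Section 14.4 states an overall 5% type I error for all planned analyses, but under the per-lens rules of 14.5 and 14.6 the worst-case bound is 10% once CLUE is counted (15% if distance and near are claimed separately)

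*Combined protocol and SAP*

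**What the plan says.** Section 14.4 makes three statements in a row. The first sets the error rate: "All planned analysis for this study will be conducted with an overall type I error rate of 5" per cent. The second is "No adjustment for multiple comparisons will be conducted unless specified otherwise". The third is "This is a pilot study and all the hypotheses are exploratory in nature". Section 14.2 also describes the study as a pilot: "This is a pilot study for assessing the test articles".

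Section 14.5 concludes superiority on the primary endpoints from 95% intervals for the least-squares means, if the "upper limit of the confidence intervals of the test lens is below +0.01 logMAR for distance and +0.17 for near". Section 14.6 has the matching rule for CLUE: "Statistical superiority will be concluded if the lower limit of the confidence intervals of the test lens is above 32 points". Both rules speak of a single lens. Neither section specifies an adjustment, a testing order or a split of alpha, so the exception clause in 14.4 is never used.

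Section 2.3 words the hypotheses for the lenses in the plural. The first reads in part "the distance, binocular, high luminance, high contrast visual performance of the two test lenses will be superior to +0.01 logMAR". Near vision is a second, separately numbered primary hypothesis, and CLUE is the secondary one.

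**The concern.** An overall type I error rate is a property of the whole set of claims. A plan that makes several unadjusted claims does not have that property merely by stating it. Here two lenses are each compared with fixed cut-offs on distance acuity, near acuity and CLUE. The plan asserts an overall 5% and, in the next sentence, gives up the usual means of achieving it.

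What is at stake is how the results would be described. A report could call a CLUE result statistically superior under a stated overall 5%, although that figure covers, at best, the primary claims. Section 14.2 says the data will be used to design later trials, so the label may travel beyond this report.

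The success rule adds to the uncertainty. Section 2.3 is plural where 14.5 and 14.6 are singular. The rule in 14.5 joins distance and near, while 2.3 lists them as two hypotheses. The number of claims that the 5% should cover is therefore not fixed.

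**Working it through.** **Inputs**
- Stated overall error: 5% for all planned analyses (14.4).
- Lenses: 2 (sections 1.1 and 5.1).
- Cut-offs: +0.01 logMAR for distance, +0.17 logMAR for near, 32 CLUE points (2.3, 14.5, 14.6).
- Intervals: 95%, read at one limit only (14.5, 14.6). Sidedness is not stated; two-sided is assumed.
- Adjustment, gating, alpha split: none.

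**Formulas**
- Error per limit: 0.05 / 2 = 0.025, one-sided.
- A claim that needs several limits at once is an intersection-union test. It counts as one claim of at most 0.025.
- For k claims, the upper bound is k × 0.025, and the value under independence is 1 − 0.975^k.

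**Can the stated 5% be reproduced?** Yes, for the primary claims alone. If a lens must meet distance and near together, there is one claim per lens: 2 × 0.025 = 5.0% (independent: 1 − 0.975² = 4.9%).

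**All superiority claims, per-lens wording**

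| Rule | Primary claims | Bound (independent) | Claims with CLUE | Bound (independent) |
|---|---|---|---|---|
| Distance and near jointly | 2 | 5% (4.9%) | 4 | 10% (9.6%) |
| Distance and near separately | 4 | 10% (9.6%) | 6 | 15% (14.1%) |

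**If the plural in 2.3 means that both lenses must pass**

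| Rule | Primary claims | Bound (independent) | Claims with CLUE | Bound (independent) |
|---|---|---|---|---|
| Each endpoint a separate claim | 2 | 5% (4.9%) | 3 | 7.5% (7.3%) |
| All four primary limits jointly; CLUE in both lenses | 1 | 2.5% | 2 | 5% (4.9%) |

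Only the last row keeps every superiority claim within 5%, and the documents do not select it.

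**Effect of correlation.** The same subjects wear both lenses, so positive correlation is plausible, but the documents give no values. The simulation used 500,000 draws per setting, assumed correlations of 0 to 0.9 between lenses and 0 to 0.5 between endpoints, and the binding means at their cut-offs. With CLUE included, the error was about 6.3% to 9.6% under the joint rule and 8.6% to 14.1% under the separate rule. Every setting exceeded 5%. The primary claims under the joint rule gave 3.5% to 5.0%.

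**How unfavourable the worst case is.** The 5% for the joint primary rule needs one endpoint exactly at its cut-off in both lenses while the other clearly passes. With distance and near both at their cut-offs in both lenses, that rule's primary error is only about 0.1% to 0.9% over the same correlations.

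**With a gate.** Suppose CLUE is tested for a lens only after that lens has met both primary limits. If the primary null holds for that lens, any false claim needs a false primary claim first, at most 0.025. If it does not hold, only CLUE can be falsely claimed, again at most 0.025. Over two lenses: 2 × 0.025 = 5%.

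All figures leave out the between-lens comparison in 14.5, where each endpoint is "analyzed separately using a linear mixed model to test for the difference between the study lens systems", because that test has no decision rule.

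**The case against.** The strongest reply is that 14.4 answers the point itself. It says that nothing is adjusted and that every hypothesis is exploratory. On that view the 5% is a level for each analysis, matching the 95% intervals, and the only fault is the word overall. Much of this stands. It excuses the lack of adjustment and keeps the point minor. It does not make the sentence true as written; if a per-analysis level was meant, the sentence should say so.

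A second reply is that 14.5 joins the two limits, so the primary claims are within 5%. That also stands. The excess arises from CLUE, or from treating distance and near as separate claims. Fitting separate models for the two endpoints does not by itself create separate claims; the better support for that reading is the numbering in 2.3.

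A reader might infer more than the documents support:
- **That the trial runs a 15% error rate.** The 15% is a union bound with all six means at their cut-offs, under the less literal reading of 14.5.
- **That the error could reach 30%.** This would need one-sided 95% limits (6 × 0.05). No text points to them; 14.5 uses the upper limit and 14.6 the lower limit of an ordinary 95% interval.
- **That inflation is being hidden.** Section 14.4 discloses the lack of adjustment openly.

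**Conclusion.** The point holds, as a minor one. The overall 5% in 14.4 is not delivered for all planned analyses under the per-lens wording of 14.5 and 14.6. The worst-case bound with CLUE is 10% (9.6% if independent) when distance and near are required together, and 15% (14.1%) when they are claimed separately. The primary claims alone stay within 5% on the literal rule in 14.5.

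This rests on two-sided 95% intervals, on CLUE being claimed for each lens, and on there being no gate, since none is stated. A different settled rule would change the figure: requiring all four primary limits jointly, with CLUE required in both lenses, would keep the superiority claims within 5%. The defect is confined to the error statement and the unaligned wording of the success rule. It does not bear on the validity of any single interval.

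**What to change.** Replace the first sentence of 14.4 with: *Each hypothesis is assessed for each lens with a two-sided 95% CI (one-sided 2.5%); the overall type I error across lenses and endpoints is not controlled.* Then make the lens wording of 2.3 agree with 14.5 and 14.6, and state whether distance and near are claimed jointly or separately. It would also help to say in 14.5 whether the between-lens comparison is inferential or descriptive.

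The cost is that a favourable-sounding error statement is dropped. No data, subjects or models change, and every per-lens claim remains available.

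If the sponsor prefers to keep an overall 5%, it can require distance and near jointly within each lens and test CLUE for that lens only after both are met. The 5% should then be stated for the superiority claims only, with the between-lens comparison outside it. The price is that a lens meeting only one primary limit could not be called superior, and its CLUE result could not be claimed.

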14.5. Primary Analysis

Primary efficacy analysis:

Visual Performance:

Near and distance binocular, high luminance, high contrast visual performance on logMAR scale will be analyzed separately using a linear mixed model to test for the difference between the study lens systems. Each model will include the experimental design factors: sequence of lens wear, lens wearing period and lens type as fixed effects. Other baseline characteristics known of importance such as age, gender, and/or add power will be included as fixed covariates when appropriate. The covariance between residual errors from the same subject across lens wearing periods will be selected based on the finite-sample corrected Akaike's Information Criterion (Keselman et al. 1998). Covariance structures considered may include: Homogenous compound symmetry (CS) and Unstructured covariance structure (UN). The structure that returns the lowest Akaike Information Criteria Corrected (AICC) will be selected as the structure that best fit the data.

Comparisons will be carried out using 95% confidence intervals constructed of least squared means (LSM) from the linear mixed models. Statistical superiority will be concluded if the upper limit of the confidence intervals of the test lens is below +0.01 logMAR for distance and +0.17 for near.

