5. TEST ARTICLE ALLOCATION AND MASKING

5.1. Test Article Allocation

The study lenses will be worn in a bilateral and random fashion using a 2x2 crossover design with 2 lens types and 2 periods. Using a computer-generated randomization scheme provided by the study biostatistician, each subject will randomly be assigned to one of two unique sequences of the two lens types (Test1/Test2 or Test2/Test1). Randomization will be stratified by site.

Permuted block randomization will be used to avoid bias in the assignment of subjects to treatment, and to enhance the validity of statistical comparisons across treatment groups. Each block will contain two different lens trial sequences.

The order of lens wear will be based on the randomization scheme assigned to the study site. The study site will follow the randomization scheme provided and will complete enrollment according to the randomization list and will not pre-select or assign subjects.

This is a single masked study: subjects will be masked to the identities of the study lenses.

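### Sections 14.5 and 14.6 read most naturally as indexing the residual covariance by wearing period, so both lenses share one averaged variance; the single-lens 95% intervals that decide the verdicts are mis-sized if the lenses differ in spread (minor)

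*Combined protocol and SAP*

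**What the plan says.** Section 5.1 sets up the study "using a 2x2 crossover design with 2 lens types and 2 periods". On the permuted blocks it adds: "Each block will contain two different lens trial sequences". The two sequences should therefore be close to equal in size.

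Section 14.5 says that near and distance acuity "will be analyzed separately using a linear mixed model to test for the difference between the study lens systems", with "sequence of lens wear, lens wearing period and lens type as fixed effects". On the residuals it says: "The covariance between residual errors from the same subject across lens wearing periods will be selected" by AICC. Compound symmetry (CS) and unstructured (UN) are named as structures that may be considered. Section 14.6 repeats the covariance wording for CLUE and adds Kenward-Roger degrees of freedom for all models. Neither section mentions lens-specific variances, a grouping option or a robust standard error.

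The decision rules concern one lens at a time. Section 14.5: "Statistical superiority will be concluded if the upper limit of the confidence intervals of the test lens is below +0.01 logMAR for distance", with +0.17 as the near limit. Section 14.6: "Statistical superiority will be concluded if the lower limit of the confidence intervals of the test lens is above 32 points".

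**The concern.** The covariance structure suits one quantity and the verdicts use another. A period-indexed matrix lets the two periods differ in variance but not the two lenses. Each period mixes both lenses, so each period variance estimates the average of the two lens variances. For the lens difference this does no harm. For a single lens's mean, the interval should reflect that lens's own variance.

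If the lenses differ in spread, the more variable one can be declared superior to its limit more often than the 2.5% implied by one limit of a 95% interval. The less variable lens faces a stricter test than intended. Neither AICC nor Kenward-Roger corrects this: both named candidates average over lenses when indexed by period, and Kenward-Roger takes the chosen structure as correct.

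**Working it through.** **Inputs from the documents**
- 2x2 crossover with both sequences in each block (5.1).
- At least 60 completers (14.2), taken as 30 per sequence.
- Per-protocol completers of all visits (14.1, 14.3), so both periods are present.
- 95% intervals of least-squares means (LSMs), with one limit deciding (14.5, 14.6).
- CLUE population SD 20 (2.2).

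**Assumption:** the ratio r of the larger to the smaller lens residual SD, taken as 1.0 to 1.5.

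**Step 1: true variance of one lens's LSM.** Sequence, period and lens saturate the four sequence-by-period cells. Ignoring covariates, LSM_A is the average of lens A's mean in period 1 of sequence AB and its mean in period 2 of sequence BA. Its variance is σA²(1/n1 + 1/n2)/4, which is σA²/N when n1 = n2 = N/2.

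**Step 2: variance the model uses.** Period-indexed UN gives LSM_A the variance (S11/n1 + S22/n2)/4. Each of S11 and S22 pools both sequences and, with equal sequences, has expectation (σA² + σB²)/2. The expected variance is therefore ((σA² + σB²)/2)/N, and it is the same for LSM_B. CS gives the same value.

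**Step 3: coverage.** Let k be the square root of (averaged variance / own variance):
- more variable lens: k = √((1 + 1/r²)/2)
- less variable lens: k = √((1 + r²)/2)

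Coverage is 2Φ(1.96k) − 1 and one-sided error is Φ(−1.96k). For example, at r = 1.25 the more variable lens has k = √((1 + 0.64)/2) = 0.906, so its one-sided error is Φ(−1.775) = 3.8%.

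| r | More variable: k | coverage | one-sided error | Less variable: k | coverage | one-sided error |
|---|---|---|---|---|---|---|
| 1.0 | 1.000 | 95.0% | 2.5% | 1.000 | 95.0% | 2.5% |
| 1.1 | 0.956 | 93.9% | 3.1% | 1.051 | 96.1% | 2.0% |
| 1.25 | 0.906 | 92.4% | 3.8% | 1.132 | 97.3% | 1.3% |
| 1.5 | 0.850 | 90.4% | 4.8% | 1.275 | 98.8% | 0.6% |

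The first row reproduces the plan's 95%, but only under equal spread.

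**Step 4: simulation.** These runs used n = 60, 200,000 trials per scenario and Satterthwaite degrees of freedom in place of Kenward-Roger.
- Equal SDs: coverage 0.950 for both lenses.
- Period-indexed: 0.929 / 0.968 (more / less variable lens) at r = 1.2 and 0.905 / 0.987 at r = 1.5.
- CS and period-indexed UN agreed to within 0.0001 with 30/30 sequences and within 0.002 with 35/25.
- UN indexed by lens: 0.949 to 0.951 for both lenses.
- Lens-difference interval under the period-indexed structure: 0.949 to 0.952 throughout.

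A smaller REML run (400 data sets, r = 1.5, two covariates, AICC choosing CS or UN) gave 0.918 / 0.990 period-indexed and 0.952 / 0.952 with lens-indexed UN. Its Monte Carlo error is about 0.01.

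**Step 5: CLUE scale, illustrative only.** Take an average SD of 20 and t(0.975, 58) = 2.002. The half-width is 2.002 × 20/√60 = 5.17 points for both lenses. With each lens's own SD it is 5.71 and 4.57 at r = 1.25, and 6.08 and 4.05 at r = 1.5. Passing the limit of 32 then needs an observed mean above 32 + 5.17 = 37.17, instead of 37.71 or 36.57 (r = 1.25), or 38.08 or 36.05 (r = 1.5). Only means in those narrow bands near 37 change the verdict. SD 20 is the spread in a population of lens wearers. Section 14.6 adjusts for baseline, so the residual SD, and with it the half-widths and bands, is likely to be smaller. These are upper illustrative values.

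**The case against.** **The index is not stated outright.** The text says which residuals are correlated, not how the matrix is ordered, and no model code is given. In this design a subject's two periods are also the subject's two lenses, and the list of structures is open. A reader might infer that the plan forbids lens-specific variances. It does not; period indexing is the natural reading, not an explicit rule. That stands, and it is why the text should name the index.

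**Unequal spread is unsupported.** Section 6.1 gives Test 1 three ADD levels and Test 2 two, plus a spherical lens. A reader might infer that one lens will be more variable, but this shows neither that nor which one. The same subjects wear both lenses, with the same modification allowance and the same dispensing criteria (7.2), which argues against a large ratio. A ratio of 1.5 means a variance 2.25 times as large, and no document supports that. Equally, Section 4.2 reports no historical clinical data on these lenses, so equal spread is not established either.

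**Verdicts seldom move.** This stands for CLUE: the bands near 37 are far from the population average of 60 in Section 2.2. The documents give no logMAR means or SDs, so the effect there cannot be placed.

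**Status of the study.** Section 14.4 calls all hypotheses exploratory and Section 14.2 disclaims a power basis. Section 14.1 already reports SDs by lens type, so a marked imbalance would be visible. These points limit the consequence. They do not make the intervals correct when the SDs differ.

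**Conclusion.** The point holds as a conditional, minor one. On the natural reading, both lenses receive essentially one averaged variance, and the single-lens intervals have their nominal 95% coverage only if the lens SDs are equal. The more variable lens's one-sided error rises from 2.5% to 3.1%, 3.8% and 4.8% at assumed SD ratios of 1.1, 1.25 and 1.5. The effect is nil at equal SDs and small at 1.1. The averaging is exact with equal sequences and nearly so at 35/25.

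A reader might go further and conclude that the plan's intervals are wrong as they stand, or that the lens comparison is invalid. The documents support neither: no lens SDs are given, and the lens-difference interval keeps its coverage under the period-indexed structure.

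**What to change.** In 14.5 and 14.6, replace the covariance sentence with wording such as: *The residual covariance of a subject's two measurements will be indexed by lens type with an unstructured matrix, so that each lens's least-squares mean and 95% confidence interval use that lens's own variance.* Keep period as a fixed effect and leave the threshold tests as they are.

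If AICC selection is retained, index both candidates by lens type, with UN allowing lens-specific variances. CS still averages the lenses whenever it is chosen, so fixing UN in advance is cleaner.

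The cost is one index in three models and one sentence in each section, with no new data, visits or subjects. The downside is a wider interval for the more variable lens: by 1/0.956, 1/0.906 and 1/0.850, or about 5%, 10% and 18%, at ratios 1.1, 1.25 and 1.5. If variance differs by period instead, nothing is lost: with equal sequences the lens-indexed variance averages the two periods, which is right for a lens mean.
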